PROTOCOL SYNOPSIS

Study Title	Intranasal oxytocin to promote weight loss in children, adolescents, and adults with brain tumors and hypothalamic obesity syndrome
Funder	Doris Duke Charitable Foundation
Clinical Phase	Exploratory therapeutic trial, Phase II
Study Rationale	
Brain tumors are the most common solid tumor in childhood (37). While rates of survival are improving, severe obesity is a frequent complication, in particular for children with tumors that affect the hypothalamus (32). Oxytocin (OXT) is a hormone that is produced in the hypothalamus (54). Although endocrinologists routinely replace other deficient hormones in children who have brain tumors, it is not current practice to replace OXT. In diet-induced obese non-human primates, chronic exogenous OXT increases total energy expenditure and inhibits food intake (11), two important physiologic targets for the treatment of brain-tumor related obesity (8, 50). In humans, OXT may promote weight loss (88) and has a favorable safety profile in both adults and children (81). Thus, the proposed study has the potential to identify a rational, effective, and safe treatment strategy for a highly morbid condition for which no alternatives currently exist. For extremely obese individuals, obesity may be entrenched and more challenging to address. Thus, anti-obesity interventions may be more effective in individuals who have not yet developed persistent obesity, as is expected given the natural history of this condition. Increased cardio metabolic risk is present even at BMI > 85thile or BMI > 25 kg/m². For this reason, we will include overweight and obese individuals. Moreover, the insights gained with respect to the pathophysiology of this highly recalcitrant form of obesity are expected to inform the development of innovative strategies to address other rare human obesity syndromes, as well as the more widespread epidemic of diet-induced obesity in children (61).

Study Objective(s)	
Primary
 
 To determine whether 8 weeks of treatment with intranasal OXT promotes weight loss in individuals with HypOb syndrome compared to 8 weeks of placebo. 
Secondary
 
 To assess the safety and tolerability of treatment with intranasal OXT over this duration To profile OXT serum levels (pulsatility profiling) following exogenous OXT vs placebo during pharmacokinetic measurements

	
 • To assess the impact of OXT on body composition and ectopic muscle fat. • To test the impact of OXT on energy intake and cognition at mealtimes, including calories consumed (test meal, 3-day diet record) and validated measures of cognition and eating behaviors. • To test the impact of OXT on energy output, including resting energy expenditure (REE), respiratory quotient (RQ), muscle mitochondrial oxidative phosphorylation (OXPHOS) capacity, body composition and muscle fat, and voluntary physical activity. • To test the impact of OXT on mental/emotional health and family function, via validated assessments. • To facilitate future mechanistic studies by banking biological specimens.
Test Article(s)	Intranasal oxytocin (Syntocinon, Novartis/Mylan Pharma) is a synthetic form of the hypothalamic hormone. This drug was previously approved in the U.S. for induction of milk let-down and was voluntarily withdrawn for lack of profitability. There were no safety concerns. The drug is currently approved and used for this indication in Europe from where it will be imported for the present study.
Study Design	Randomized, double-blinded, placebo-controlled, cross-over trial.
Subject Population	Inclusion Criteria
Key Criteria for Inclusion and Exclusion:	
 1) Proficient in English. 2) Males or females age 10 to 35 years, inclusive. 3) Weight \geq 51 kg 4) Girls must have a negative urine/serum pregnancy test and post-menarchal girls must use an acceptable method of contraception, including abstinence, a barrier method (diaphragm or condom), Depo-Provera, or an oral contraceptive, for the duration of the study. 5) Hypothalamic obesity, defined for the purposes of this protocol as: 
 - previously diagnosed with a brain tumor* - currently overweight or obese (BMI $>$85%ile for age/sex for $<$ 18 years, BMI $>$ 25 kg/m² for 18 – 35 years) - has at least one other endocrinopathy, indicating hypothalamic damage

-
- rate of annualized weight gain during any 6 month period (given variability in clinical course) preceding or after diagnosis and treatment greater than 2 standard deviations above population reference ranges for age and sex (45).
- 6) At least 6 months since completion of therapy with stable disease/lack of recurrence.
 - 7) Stable (dose adjustments of $\leq 20\%$ allowed) for at least 2 months on any pituitary replacement (e.g., glucocorticoid, thyroid hormone, estrogen/progestin or testosterone, growth hormone).

*Desmopressin is not required to be stable for at least 2 months. Even when taken as directed, duration of effect can vary. Participants with DI, taking desmopressin, are required to have intact thirst and be well-controlled on their current dosing regimen.
 - 8) Stable (no dose adjustments) for at least 2 months on any appetite-modulating medications (e.g., stimulants).
 - 9) Be able to ambulate independently.
 - 10) Parental/guardian permission (informed consent) and child assent.

*In hypothalamic obesity related to brain tumors, it is the damage to the hypothalamus caused by the tumor itself, or its treatment (surgery or radiation) that leads to excess weight gain. The majority of such tumors will be craniopharyngioma; a minority will be hypothalamic astrocytomas, germinomas, or other lesions. Given the overall rarity of these tumors, it is not practical to stratify by tumor type or recruit children with only one tumor type. Instead, we will minimize clinical heterogeneity by applying the criteria proposed above with respect to endocrinopathies (indicating hypothalamic damage) and rapid weight gain.

Exclusion Criteria

Exclusion criteria and AEs will be defined based on Common Terminology Criteria for AEs (CTCAE), version 4.0 (33).

- 1) Diabetes insipidus without intact thirst mechanism (i.e., history that participant is not thirsty when hypernatremic and/or continues to be thirsty when hyponatremic, by participant/family and/or practitioner report and medical records) and/or “brittle” diabetes insipidus, defined as requiring >1 admission in the past year and/or any admission within the previous 3 months.

Laboratory values: <130 or >150 mEq/L

- 2) Diabetes mellitus requiring insulin or insulin secretagogue.

Laboratory values: HgbA1c \geq 8%

- 3) Cardiovascular condition, as defined as any of the following: i) abnormal blood pressure, defined as <3%ile or >97%ile for age, sex and height (39) for adult participants abnormal blood pressure is defined as Stage 2 hypertension (systolic BP \geq 160 mm Hg or diastolic BP \geq 100 mm Hg); ii) history of cardiac arrhythmia or arrhythmia detected on screening ECG; iii) history of heart failure and/or cardiomyopathy; iv) prolonged QTc interval (QTc > 460 msec), and/or long QT syndrome phenotype and/or positive genotype for long QT syndrome pathogenic mutations.
- 4) Concurrent chronic use of medications known to prolong QTc interval and pose high risk for Torsades de Pointes (TdP) according to the current information available (www.crediblemeds.org). Concomitant medications will be assessed by IDS pharmacist, in collaboration with study cardiologist, if additional clarification is needed. In addition, we require that potential participants be on a stable dose for at least 2 months of any medication with the potential to alter cardiac rhythm to ensure the screening ECG reflects steady-state physiology.
- 5) History of liver disease, with screening laboratory studies:
Laboratory values: ALT/SGPT > 3.0X ULN or AST/SGOT > 3.0X ULN
- 6) History of chronic kidney disease, with screening laboratory studies:
Laboratory values: eGFR < 60 mL/min/1.73m², as defined by the Schwartz formula (71)
- 7) Clinically significant anemia, with screening laboratory studies:
Laboratory values: Hemoglobin < 10 g/dL
- 8) Seizure in the past 12 months.
- 9) History of gastrectomy, gastric bypass, small or large bowel resection.
- 10) History of active substance abuse.

-
- 11) Current psychotic disorder and/or suicidality.
 - 12) Supra-physiologic (>15 mg/m²/day) prescribed doses of hydrocortisone equivalent.
 - 13) Anticipated clinical plan to initiate or modify pituitary hormone replacement and/or appetite-modulating drugs during the course of the study, at the time of enrollment. After enrollment, changes to pituitary hormone replacement will be as outline in Section 4.8.
 - 14) Any investigational drug use within 30 days prior to enrollment.
 - 15) Pregnant or lactating females.
 - 16) Individuals with a known sensitivity to either oxytocin or the components of its formulation.
 - 17) Inability to take an intranasal medication (e.g., recent injury).
 - 18) Parents/guardians or subjects who, in the opinion of the Investigator, may be non-compliant with study schedules or procedures.

If vital signs and/or laboratory tests initially indicate ineligibility, select metrics may be repeated, and if eligibility is then demonstrated on repeat, subject will be enrolled. Subjects that do not meet all of the enrollment criteria may not be enrolled. Any violations of these criteria must be reported in accordance with IRB Policies and Procedures.

Number Of Subjects	N = 150 enrolled participants (Children’s Hospital of Philadelphia); because parents are engaged in research, we anticipate 150 participant-parent/legal guardian dyads, N = 20 participants with complete data. Adult participants, living independently, may enroll individually.
Study Duration	Each subject’s participation will last approximately 7 months. The entire study is expected to last 3 years.
Study Phases Screening Study Treatment	Participants will undergo a telephone screening and then, within 4 weeks, complete an in-person screening visit to determine eligibility. Then, within 4 weeks they will be randomized and begin 8 weeks of treatment with either OXT or placebo. After a 4-week “washout,” participants will cross-over to 8 weeks of treatment with the other condition (i.e., placebo or OXT).

Efficacy Evaluations	Efficacy will be evaluated for each subject by the difference in body weight over the 8 weeks while on OXT versus the 8 weeks while taking placebo.
Pharmacokinetic Evaluations	During one of the CHPS-monitored doses of each of OXT and placebo, serial peripheral blood measurements of OXT will be made.
Safety Evaluations	i) Heart rate and blood pressure during CHPS-monitored doses of OXT/placebo; ii) EKG; iii) serum sodium; iv) any need to adjust synthetic vasopressin therapy for diabetes insipidus; v) safety monitoring uniform report form (SMURF) assessments (including potential symptoms such as fluid retention, nausea/vomiting, nasal irritation)
Statistical And Analytic Plan	The within-subject effect of OXT (versus placebo) on weight change over 8 weeks will be assessed using linear mixed-effects model with the outcome being the difference of the post-treatment weight between two periods (treatment vs. placebo), adjusted for the difference of the baseline weight between the two periods as covariate.
DATA AND SAFETY MONITORING PLAN	The PI will be responsible for data quality management and ongoing safety assessment. A DSMB will be convened and will meet as per DSMB charter.

Title: Intranasal oxytocin to promote weight loss in children, adolescents and adults with brain tumors and hypothalamic obesity syndrome

NCT: NCT02849743

Date: 30-June-2021

This document describes our plans and rationale for analysis of the intranasal oxytocin (OXT) weight loss trial data (NCT02849743). This document has been generated before un-blinding. Specifically, we review the a priori defined primary and secondary outcomes, and provide the preplanned analysis including sensitivity analyses to support the findings reported in the main text. We offer these details to further the goals of reproducible research. Analyses were performed with RStudio (v.1.4.1103).

1.0. Definition of the Endpoints

1.1. The primary endpoint will be the change in body weight over 8 weeks during OXT versus placebo treatment.

1.2. Secondary endpoints will include the following:

- Cognitive restraint (stop-signal task) after monitored dose of OXT versus placebo
- Calories consumed (as a percentage of calories offered) during a test meal after a monitored dose of OXT versus after a monitored dose of placebo
- The change in arm circumference, over 8 weeks during OXT versus placebo
- The change in waist circumference, over 8 weeks during OXT versus placebo
- The change in hyperphagia (Hyperphagia Questionnaire), hunger, disinhibition of eating, cognitive restraint (Eating Inventory), mental/emotional health and quality of life (Neuro-QOL), family function (FAD-GRS) over 8 weeks during OXT versus placebo
- Fat mass, lean mass, and % body fat (DXA) at the conclusion of 8 weeks OXT versus 8 weeks of placebo
- Resting energy expenditure (REE) at the conclusion of 8 weeks OXT versus 8 weeks of placebo
- Respiratory quotient (RQ) at the conclusion of 8 weeks OXT versus 8 weeks of placebo
- Usual energy intake (calories/day via self-reported 3-day diet record) at the conclusion of 8 weeks OXT versus 8 weeks of placebo
- Change in self-reported physical activity (via BMDCS-PA questionnaire) during 8 weeks of OXT versus 8 weeks of placebo
- OXT pulse profiling after exogenous OXT vs placebo
- Safety and tolerability of OXT based on AEs

2.0 Statistical Analysis

2.1. Primary Analysis:

For the primary outcome, i.e., the change in body weight during each treatment block, linear mixed-effects modeling will be performed to assess the effect of OXT on the outcome as compared to placebo. The primary model will include the treatment (i.e., OXT vs. PBO), the randomization sequence (OXT-PBO vs. PBO-OXT), and the starting body weight in each treatment block as a time-varying covariate. We will test for a carryover effect by including the interaction of treatment by sequence in the model. This interaction term will NOT be included in the primary model if it is not significant (i.e., $p > 0.05$). (**Table 4**)

2.2. Secondary Analysis:

Similar modeling approaches will be applied to the secondary outcomes that are continuous and measured in both Blocks as in the Primary Analysis (**Supplementary Table**).

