2.3. Additional Sensitivity Analyses

We will test the effect of sequentially adding age, gender, as well as the adherence to treatment to the primary model as sensitivity analyses to understand the extent to which these may influence the main result. Adherence is defined in two ways that capture different dimensions of likely effect: first, the average % of doses consumed as compared to prescribed during each treatment block, and second, the % of days during each block with complete adherence. In exploratory analyses, we will also test the extent to which hypothalamic damage (as reflected by the presence or absence of diabetes insipidus, and by centralized MRI-based assessment of hypothalamic damage) impacts response to treatment.

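### The SAP's carryover test cannot separate carryover from a period effect; period is not otherwise modelled, and no primary contrast is named if the term is kept

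*SAP*

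**What the plan says.** SAP section 2.1 sets up a linear mixed model "to assess the effect of OXT on the outcome as compared to placebo". The outcome is weight change in each block. The listed terms are treatment, randomization sequence and the starting weight of each block. Carryover is handled by a pre-test: "We will test for a carryover effect by including the interaction of treatment by sequence in the model". The rule that follows is: "This interaction term will NOT be included in the primary model if it is not significant", with 0.05 as the threshold. The section does not say which treatment effect is primary when the term stays in.

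No period or block factor is listed elsewhere. The protocol synopsis (Statistical And Analytic Plan) models the between-period difference in post-treatment weight, "adjusted for the difference of the baseline weight between the two periods as covariate". SAP section 2.3 proposes "sequentially adding age, gender, as well as the adherence to treatment to the primary model". SAP section 2.2 extends the approach: "Similar modeling approaches will be applied to the secondary outcomes that are continuous and measured in both Blocks". Some of those outcomes are end-of-block levels rather than changes, for example "Fat mass, lean mass, and % body fat (DXA) at the conclusion of 8 weeks OXT versus 8 weeks of placebo".

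**The concern.** In a two-sequence, two-block cross-over, sequence and treatment together determine the block. The treatment-by-sequence interaction is therefore the period contrast under another name. The plan labels it carryover and lets its p-value decide whether the model is adjusted for period.

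Three things are at stake:

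- **The carryover conclusion.** An ordinary time difference can be reported as OXT carryover, which would cast unwarranted doubt on the trial's own result. Real carryover offset by a time difference can go unseen.
- **The period adjustment.** It is made only when a low-powered test happens to be significant.
- **The primary contrast.** A model with the interaction yields an OXT effect for each sequence as well as their average. Each one-sequence effect is confounded with period.

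For weight change, a steady gain cancels between blocks. It does not cancel for end-of-block outcomes such as DXA or resting energy expenditure, measured 12 weeks apart (4-week washout plus 8-week block), in participants who are still growing. The age range is 10 to 35 years. The documents do not give the size of that growth, and section 2.2 says only that the models will be similar.

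**Working it through.** **Inputs.** From the documents: two sequences, two 8-week blocks, a 4-week washout, the 0.05 threshold, and "N = 20 participants with complete data" (protocol synopsis). SAP section 2.4 says the recruitment goal was missed but gives no number, so n = 10 is run as well. Assumed: period effects, carryover sizes and sequence splits, all in SDs of the within-participant OXT minus placebo (PBO) difference; two-sided tests. The plan gives no figure of its own to reproduce on this point.

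**Step 1: what the interaction estimates.** Let τ be the OXT effect, π the block 2 minus block 1 effect, and λ the carryover of OXT into a following placebo block, all given starting weight. Placebo carryover is taken as zero.

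| Sequence | Block 1 | Block 2 | OXT minus PBO |
|---|---|---|---|
| OXT-PBO | μ₁ + τ | μ₁ + π + λ | τ − π − λ |
| PBO-OXT | μ₂ | μ₂ + π + τ | τ + π |

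- Interaction (difference of the last column): (τ + π) − (τ − π − λ) = 2π + λ.
- Sequence-averaged effect: half the sum = τ − λ/2.

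The matrix with intercept, treatment, sequence and interaction has rank 4, and still 4 after adding period. Block starting weight does not break the alias. On one simulated data set of 20 participants, the mixed model with the interaction and the one with period gave the same log-likelihood (−77.06775) and the same p-value (0.8816).

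**Step 2: how often carryover is declared when there is none.** The standard error of the interaction is √(1/n₁ + 1/n₂), with n − 2 degrees of freedom. At 10/10 it is √0.2 = 0.447, so π = 0.5 gives noncentrality 1/0.447 = 2.24. At 5/5 it is √0.4 = 0.632, giving 1/0.632 = 1.58. Noncentral-t flag rates:

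| π (SD) | 0 | 0.1 | 0.25 | 0.5 | 1 |
|---|---|---|---|---|---|
| n = 20 | 5% | 7% | 19% | 56% | 99% |
| n = 10 | 5% | 6% | 11% | 29% | 79% |

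Conversely, λ = 1 with π = −0.5 gives 2(−0.5) + 1 = 0. The flag rate is then 5%, although the treatment estimate is biased by −λ/2 = −0.5 SD.

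**Step 3: the primary test under the keep/drop rule, sequence-averaged contrast** (200,000 simulated trials per setting). If the term is dropped, the estimate weights the sequences by their numbers. It then differs from the period-adjusted estimate by −(n₁ − n₂)/(2n) times the observed interaction. At 12/8 the factor is 4/40 = 0.10, and at 6/4 it is 2/20 = 0.10. Averaged over keeping and dropping, with effects of 0.660 SD (n = 20) and 0.996 SD (n = 10) for power:

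| Split | π | Bias | Power, SAP rule | Power, period always fitted |
|---|---|---|---|---|
| 10/10 | 0.5 | 0 | 79% | 80% |
| 12/8 | ±0.5 | 0.03 SD | 81% or 74%, by direction | 78% |
| 6/4 | ±0.5 | 0.05 SD | 82% or 72%, by direction | 77% |

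Type I error is about 5% with balanced sequences and about 5.5% at 12/8.

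**Step 4: if a one-sequence coefficient is read instead.** Ordinary 0/1 coding prints the OXT effect in one sequence when the interaction is kept. At π = 0.5 the overall type I error is then about 31% (n = 20) or 16% (n = 10). At π = 0.1 it is about 7% for both.

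**The case against.** The best counter-argument is that little of this reaches the primary result. The SAP's wording most naturally means the sequence-averaged contrast, and on that reading balanced sequences give no bias and near-nominal type I error. At 12/8 the power under the SAP rule averages (81 + 74)/2 = 77.5% over the two directions, against 78% with period fitted, so power is no reason to change. This stands.

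The high error rates in step 4 need a reading that the SAP does not state. That also stands. They show why the contrast should be named, and are not an expected error rate.

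Every effect size is assumed, and for weight change a steady trend cancels, so a 0.5 SD period effect has no identified source. That is fair, and the sizes should be read as a range. The interaction is also not blind to carryover: λ = 1 with π = 0 is flagged in about 56% of trials at n = 20. The fault is that it cannot separate the two.

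Only the protocol synopsis is available, and it refers to a section that is not shown; nor are the SAP's Table 4 and Supplementary Table. A period term could be mentioned there. The SAP nevertheless lists its primary model terms explicitly, and its test and dropping rule are wrong for their stated purpose whatever those pages contain.

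**Conclusion.** The concern holds and should be fixed. The alias is exact and needs no assumption. Nor do the other two points, for the text available: no period term is pre-specified, and no primary contrast is named for the case where the interaction is kept.

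The main damage is to the carryover statement, which neither supports a finding of carryover nor gives reassurance against it. A period effect of about 0.46 SD (n = 20) or 0.71 SD (n = 10) is enough for an even chance of a false carryover report. The effect on the primary treatment test is small if sequences are roughly balanced and the averaged contrast is used. It grows with imbalance: at π = 0.5, type I error is about 7% at 7/3 and 8.4% at 14/6, but nothing in the documents points to such splits.

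**What to change.** In SAP section 2.1, delete the interaction and the p > 0.05 rule. Pre-specify one mixed model with treatment, period, sequence and block starting weight. Name the sequence-averaged OXT minus PBO effect as the primary contrast. Report the sequence term descriptively only, with no part in model selection; block 2 starting weight by sequence would be useful descriptive support. Use the same model for the continuous secondary outcomes measured in both blocks.

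The SAP should also say that protection against true carryover rests on the 4-week washout. The bias of −λ/2 remains under the new model. With λ = 1, π = −0.5 and no treatment effect, false positives are about 56 to 58% at n = 20 with or without the period term.

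The cost is a wording change and one degree of freedom, with no new data. If there is no period effect and power without the term is 80.0%, power with it is:

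| n = 20 split | Power | n = 10 split | Power |
|---|---|---|---|
| 10/10 | 79.8% | 5/5 | 78.7% |
| 12/8 | 78.1% | 6/4 | 77.1% |
| 13/7 | 76.0% | 7/3 | 71.6% |
| 14/6 | 72.6% | | |

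The SAP says it was written before unblinding. If unblinding has since taken place, the new model should be reported as a disclosed change.
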